### PROTOCOL SUMMARY

Title:	A Phase 2/3 Double Blinded, Randomized, Placebo-Controlled Study in Healthy Adult Volunteers in Vietnam to Examine the Safety and Immunogenicity of a Seasonal Trivalent Inactivated Split Virion Influenza Vaccine (IVACFLU-S) produced by IVAC
Description of Study Design:	
This is a phase 2/3, double-blind, placebo-controlled trial of 888 adults, ages 18 to 60 years old randomized to receive vaccine or placebo according to schema below. Phase 2 will be conducted at 1 site of Long An (252 subjects). Following a determination of safety of vaccine in phase 2 study by Protocol Safety Review Team (PSRT) review and with approval from Vietnam Ministry of Health (MOH), Phase 3 enrollment will commence at 2 sites, Long An (252 subjects, including 210 vaccine recipients and 42 placebo recipients) and Dong Nai (384 subjects, including 320 vaccine recipients and 64 placebo recipients).
 
Safety will be assessed in all Phase 2 and 3 participants through Day 91. Safety data till Day 8 post-vaccination from the phase 2 study will be presented to Protocol Safety Review Team (PSRT) for evaluation and an interim report will be filed with local institutional review board (IRB) and MOH. Immunogenicity will be assessed only in Phase 3 participants. Blood samples will be collected in a subset of 252 individuals (210 vaccine recipients and 42 placebo recipients) randomized at one of the study sites to get evaluable samples from at least 200 vaccine recipients (100 each from both age groups) and 40 placebo recipients (20 each from both age groups) 21 days after vaccination.
 
Approximate participant distribution based on age, study arm and study will be as follows:

Study Hypothesis:	Age group	IVACFLU-S	Placebo	Total	
	Phase 2				
	18 - 45	105	21	126	
	46 - 60	105	21	126	
	Phase 3				
	18 - 45	265	53	318	
	46 - 60	265	53	318	
	Safety:				
	A single dose of seasonal trivalent inactivated split virion influenza vaccine (IVACFLU-S) will be safe and well tolerated in adults 18 to 60 years of age.				
	Immunogenicity:				
	A single dose of seasonal trivalent inactivated split virion influenza vaccine (IVACFLU-S) will induce immune responses to each of the three vaccine antigens to meet one or both age group specific Vietnam Ministry of Health (MOH) licensure requirements.				
		Criteria	18 – 45 year old	46 – 60 year old	
	Seroprotection (HAI $\geq 1:40$ )	$\geq 70\%$	$\geq 60\%$		

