### **Secondary Immunogenicity Endpoints:**

The secondary immunogenicity endpoints will be analyzed by the following:

- A. Number and percentage of participants who develop at least a four-fold increase in HAI antibody titer to each of the vaccine antigen post vaccination measured on Day 22 by pre-vaccination HAI antibody titer of <1:10 or  $\geq 1:10$ .
- B. Geometric mean titers (GMTs) of serum HAI antibodies pre- (Day 1) and post vaccination (Day 22) for each of the 3 vaccine antigens by pre-vaccination HAI antibody titer of <1:10 or  $\geq 1:10$ .
- C. Geometric mean fold rises (GMFRs) of serum HAI antibodies (post vaccination/pre-vaccination) for each of the 3 vaccine antigens by pre-vaccination HAI antibody titer of <1:10 or  $\geq 1:10$ .

The licenture requirements are based on on the point estimate of response in the vaccine group and are not based on comparison to a control. So there will be no formal statistical testing to compare immune response between vaccine and placebo. There are two types of immunogenicity measurements against each of the 3 vaccine antigens, percentages of subjects with immune response and Geometric Mean Titers (GMT) that will be used to evaluate this study objective. For each percentage of subjects with the defined immune responses, the percentage and its corresponding 2-sided exact (Clopper-Pearson) binomial 95% confidence interval (95% CI) around the percentage will be computed for each treatment group and by age group. GMT along with the corresponding two-sided 95% CIs, by exponentiating the corresponding log-transformed means and their 95% CIs, will be summarized by treatment group on Day1 and Day 22. The same approach will be used to summarize GMFR of Day 22/Day1 separately by treatment group and age group.

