## 6.6 STATISTICAL TESTS

The default significance level will be 5%, confidence intervals will be 95%, and all tests will be two-sided, unless otherwise specified in the description of the analyses.

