## 7.4 MULTIPLE COMPARISONS/ MULTIPLICITY

No multiplicity adjustment to the Type 1 probability of error, alpha, will be made for the multiple testing of immunogenicity endpoints corresponding to the three vaccine antigens under the intersection-union property. That is, the immune responses to each of the three vaccine antigens induced by IVACFLU-S seasonal trivalent split inactivated influenza vaccine need to meet Vietnam Ministry of Health licensure requirements.

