## 16. IMMUNOGENICITY ANALYSIS

### 16.1 STATISTICAL CONSIDERATIONS

The Vietnam MOH guidance on serological immune response requirements for influenza vaccine is a modification of the EMEA/CPMP serological criteria for assessing seasonal influenza for licensure. The age-group specific MOH licensure requirements for influenza vaccine in adults are shown in Table 3.

Table 3 Vietnam MOH Criteria for Evaluation of Influenza Vaccine Immune Responses

	Age Group	
	18 – 45	46
Proportion achieving a HAI titer $\geq$ 1:40 (seroprotection)	$\geq$ 70%	$\geq$ 60%
Proportion achieving at least 4 fold rise in HAI titer (seroconversion)	$\geq$ 40%	$\geq$ 30%
GMT rise in HAI titer	$\geq$ 2.5 times	$\geq$ 2.0 times

Null hypothesis ( $H_0$ ):

A single dose of IVACFLU-S seasonal trivalent split, inactivated influenza vaccine will not induce immune responses to each of the three vaccine antigens to meet one or both age group specific Vietnam Ministry of Health licensure requirements i.e., as mentioned in Table 3.

Alternative hypothesis ( $H_1$ ):

A single dose of IVACFLU-S seasonal trivalent split, inactivated influenza vaccine will induce immune responses to each of the three vaccine antigens to meet one or both age group specific Vietnam Ministry of Health licensure requirements i.e., as mentioned in Table 3.

Of the three criteria, seroconversion has been the most frequent criteria not meeting licensure threshold. Though the study assumption is based on Phase 1 immunogenicity data for adults 18-45 years of age, we anticipate the immune response in those 46 - 60 will be comparable since significant decline in antibody response is most associated with those who are  $\geq$ 65 years of age.

Taken together with the immunogenicity results of the IVACFLU-S phase 1 study (refer to [Section 2.1.6](#) in the protocol), the sample size consideration for immunogenicity for the study was based on the precision of the estimate of percent of vaccine recipients with HAI seroconversion and seroprotection responses. With a sample size of 100 evaluable vaccine recipients from each age group, the study provides the precision of immunogenicity response as estimated by width of 95% CI of  $\leq \pm 10.2\%$  around the range of estimated response rate ([Table 4](#))

Document:	\\EEDC-NAS01A\Biosdata\Path\IVACFLU-S\IYA06804\Biostatistics		
	Documentation\SAP\IVACFLU-S-0203_SAP_Draft v1.0		
Author:	[name]	Version Number:	1.0
		Version Date:	[11AUG2017]

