### 16.1.1 PROBABILITY FOR DEMONSTRATING SEROCONVERSION CRITERIA FOR LICENSURE

For the 18-45 year old cohort, if the true seroconversion response to each strain is  $\geq 49\%$ , then there is 91% probability that the point estimate for seroconversion to all three strains will be  $\geq 40\%$ .

Likewise, if the true seroconversion response to each strain is  $\geq 60\%$ , then there is 92% probability that the lower bound of the exact 95% CI for seroconversion to all strains will be  $\geq 40\%$ . For the older age cohort (46-60 years old), if the true seroconversion response to each strain is  $\geq 39\%$ , then there is 93% probability that the point estimate for seroconversion to all three strains will be  $\geq 30\%$ . Given that the lowest seroconversion response in the IVAC Phase 1 trial was to B viral strain at 76.7% (95% CI, 57.7-90.1), there is high probability (Table 5) of demonstrating age group specific seroconversion requirement with a sample size of 100 evaluable participants per age group who received the study vaccine.

Table 5: Probability of demonstrating seroconversion response to all 3 viral strains by age groups and assumed true response to each viral strain.

Age group (point estimate response)	True response		
	Probability > 90%	Probability > 95%	Probability > 99%
18-45 ( $\geq 40\%$ )	$\geq 49\%$	$\geq 51\%$	$\geq 54\%$
46- 60 ( $\geq 30\%$ )	$\geq 39\%$	$\geq 40\%$	$\geq 43\%$

Document: \\EEDC-NAS01A\Biosdata\Path\IVACFLU-S\IYA06804\Biostatistics  
Documentation\SAP\IVACFLU-S-0203\_SAP\_Draft v1.0

Author: [name]

Version Number:

1.0

Version Date:

[11AUG2017]

Template No: CS\_TP\_BS016 Revision 4  
Effective Date: 01Apr2016

Reference: CS\_WI\_BS005

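### Does the Phase 3 immunogenicity hypothesis need a formal test behind its alpha and intersection-union wording?

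*Combined protocol and SAP*

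**What the plan says.** SAP section 16.1 frames the question as a hypothesis test. H0 and H1 differ on whether one dose induces responses to each of the three antigens "to meet one or both age group specific Vietnam Ministry of Health licensure requirements", and both refer to Table 3. That table lists three MOH criteria by age group: seroprotection (70% for ages 18-45, 60% for 46-60), seroconversion (40% and 30%) and GMT rise (2.5 and 2.0 times). The same section remarks: "Of the three criteria, seroconversion has been the most frequent criteria not meeting licensure threshold". The Protocol Summary and protocol section 13.1 word the hypothesis in almost the same way ("to meet one or both age group specific Vietnam Ministry of Health (MOH) licensure requirements" in the Summary).

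SAP section 6.6 gives a general default: "The default significance level will be 5%, confidence intervals will be 95%, and all tests will be two-sided". Section 7.4 then says that no multiplicity adjustment to "alpha, will be made for the multiple testing of immunogenicity endpoints corresponding to the three vaccine antigens under the intersection-union property", and explains that the response to each antigen has to meet the MOH requirements.

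The basis for licensure is in protocol section 13.8, under the secondary immunogenicity endpoints, where the requirements are said to be "based on on the point estimate of response in the vaccine group and are not based on comparison to a control". SAP section 3.3 declares no change from the protocol, and SAP Tables 5 and 6 are labelled by point-estimate response. SAP sections 16.1.1 and 16.1.2 also give, for ages 18-45 only, the probability that the lower confidence bound clears the threshold, but no decision rests on it. SAP section 16.2 plans rates, GMTs and GMFRs with 95% confidence intervals and names no test of any of them against a threshold.

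**The concern.** An intersection-union procedure has level alpha only if every component does. Requiring an observed rate to reach a threshold is not a level-alpha test of the true rate, because it succeeds about half the time when the truth sits on the threshold. The text in section 7.4 therefore fits neither reading. If the observed rate is the requirement, there is no Type 1 error to control. If the true rate is meant, the rule does not control it.

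Two looser ends add to the unease. Neither document says outright that all three criteria in Table 3 must be met. And the one-or-both phrase can be read as a union over age groups, which section 7.4 does not address.

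This is the primary immunogenicity hypothesis of Phase 3. The worry is a study report that announces rejection of H0 with no adjustment needed when no test was done, or that calls H1 satisfied with one age group or one criterion failing.

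**Working it through.** **Inputs.** There are 100 evaluable vaccine recipients per age group (SAP section 16.1), drawn from a bled subset of "252 individuals (210 vaccine recipients and 42 placebo recipients) randomized at one of the study sites", which is 210/2 = 105 vaccinees per age group. Thresholds are those in SAP Table 3. The strains are treated as independent within a person wherever a joint figure is given; the plan says only that responses to each strain were simulated as binomial.

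**Reproducing the plan.** With X ~ Bin(100, p), the point-estimate rule passes when X ≥ 100 × threshold. The probability for all three strains is P(X ≥ r)³.

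| Criterion, age group | True rate | P(one strain) | Cubed | SAP states |
|---|---|---|---|---|
| Seroconversion 18-45, X ≥ 40 | 49% | 0.9717 | 91.7% | 91% |
| Seroconversion 46-60, X ≥ 30 | 39% | 0.9759 | 92.9% | 93% |
| Seroprotection 18-45, X ≥ 70 | 78% | 0.9768 | 93.2% | 92% |
| Seroprotection 46-60, X ≥ 60 | 69% | 0.9782 | 93.6% | 93% |

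For the lower-bound statements (ages 18-45), the smallest count whose two-sided 95% Clopper-Pearson lower limit reaches the threshold is 51 for seroconversion and 80 for seroprotection. Then P(X ≥ 51 | 0.60)³ = 0.9729³ = 92.1% (stated 92%), and P(X ≥ 80 | 0.87)³ = 0.9828³ = 94.9% (stated 95%). The plan's figures are sound.

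**Error rate of each rule.** The intersection-union size is the pass probability when one strain lies exactly on its threshold and the others are certain to pass.

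| Criterion, age group | Point-estimate rule | Lower-limit rule (cut-off) |
|---|---|---|
| Seroconversion 18-45 | 0.538 | 0.0168 (51) |
| Seroconversion 46-60 | 0.538 | 0.0210 (40) |
| Seroprotection 18-45 | 0.549 | 0.0165 (80) |
| Seroprotection 46-60 | 0.543 | 0.0248 (70) |

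So the stated rule is nowhere near 5% or 2.5%. A lower-limit rule would be at or below 2.5% per component, and section 7.4 would then be literally correct. Even so, counting success in either age group would exceed 2.5% across the two: 1 − (1 − 0.0168)(1 − 0.0210) = 0.037 for seroconversion, and by the same formula 0.041 for seroprotection.

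GMT rise cannot be treated in this way, because the documents give no standard deviation.

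**Does any output depend on this?** The planned immunogenicity outputs are counts, percentages, GMTs and GMFRs with intervals, plus listings, reverse cumulative distribution curves and GMT plots. The table shells for seroconversion, seroprotection, GMT and GMFR have no p-value column. Deleting or keeping the alpha wording leaves every number the same.

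**Which criteria, which age groups?** H1 points to Table 3 as a whole, and the remark about seroconversion treats each of the three as a threshold that can be missed. SAP sections 16.1.1 and 16.1.2 then assess seroconversion and seroprotection each as a requirement. All three applying is the natural reading. The thresholds differ by age group, the primary endpoints are defined by age group, and SAP section 7.5 requires the analyses by age group. The one-or-both phrase then describes two separate claims, either or both of which may succeed. No pooled success claim has a threshold to be judged against.

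**Where Phase 1 points.** At the lowest Phase 1 rates (76.7% seroconversion and 93.3% seroprotection, both for strain B), both rules pass with probability above 0.999 per strain at n = 100, in either age group.

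**The case for a change.** The strongest case for acting is that the SAP itself speaks of multiple testing of immunogenicity endpoints, so it is not enough to reply that no formal testing is planned. The statement in protocol section 13.8 rules out only a vaccine-versus-placebo test. The two rules can also part company. If every strain had a true seroprotection rate of 77.9%, the lower Phase 1 confidence limit for strain B, the 18-45 group would pass the point-estimate rule on all three strains with probability 0.9754³ = 92.8%, but the lower-limit rule with only 0.3572³ = 4.6%.

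The first part stands: the language in sections 7.4 and 16.1 has no test behind it, and tidier drafting would have left it out. The second part is true but does not point to a fault. The gap between the rules measures the strictness of the MOH criterion, which the plan is entitled to use because licensure is decided on it. Adopting the lower-limit rule would demand more than the regulator does (51 rather than 40 responders, or 80 rather than 70, in ages 18-45), and the plan offers no operating characteristics for that rule in ages 46-60. That is a choice of stringency, with a cost in pass probability, and not the repair of an error.

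A sentence restating the required criteria and the age-specific conclusions would be harmless. It would record what an analyst reading Table 3 and section 7.5 would do anyway. The authoritative rule on which criteria bind lies in the MOH guidance, which is not among the documents here.

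**Conclusion.** No change follows. The observation is accurate as a matter of wording: a point-estimate rule with size 0.538 to 0.549 at n = 100 is not a level-alpha test, so the references to alpha and the intersection-union property are decorative. The substance is right. All three strains must pass, so no adjustment across strains is called for. The licensure check is on the observed rate as the protocol says, the planned intervals show the uncertainty, and no estimate, p-value or MOH decision depends on the loose phrases. The remaining risk is an overstatement in the study report, visible to any reader who sees that no test was run.

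This conclusion assumes that the MOH does decide on point estimates, as protocol section 13.8 states. It also assumes that Table 3 is read as three joint criteria, with a separate conclusion for each age group. The single-strain figures do not depend on how strains are correlated; the three-strain figures assume independence, and positive correlation would raise them.

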## 7.5 EXAMINATION OF SUBGROUPS

1. All safety and immunogenicity analyses will be conducted for subgroups of age category i.e., 18-45 and 46-60.
2. Analysis of secondary immunogenicity endpoints, Phase 3, will be conducted for subgroups of pre-vaccination HAI antibody titer i.e., <1:10 or  $\geq$  1:10 and subgroups of age category i.e., 18-45 and 46-60.

## 8. OUTPUT PRESENTATIONS

The shells provided with this SAP describe the presentations for this study and therefore the format and content of the summary TLFs to be provided by QuintilesIMS Biostatistics.

Tables and figures will be presented for Phase 2 and Phase 3 subjects combined and pooled across study sites with the below exceptions:

- Subject disposition summaries will be reported separately by study site, in addition to being pooled across study sites.

---

Document:	\\EEDC-NAS01A\Biosdata\Path\IVACFLU-S\IYA06804\Biostatistics		
	Documentation\SAP\IVACFLU-S-0203_SAP_Draft v1.0		
Author:	[name]	Version Number:	1.0
		Version Date:	[11AUG2017]
Template No:	CS_TP_BS016 Revision 4	Reference:	CS_WI_BS005
Effective Date:	01Apr2016		

- Immunogenicity measurements will be from Phase 3 subjects at the Ben Luc site only; thus immunogenicity TLFs will be restricted to this subset.

All table and figure summaries will be presented by treatment group both by age group (18-45, 46-60) and pooling across age groups. Additionally, for secondary immunogenicity endpoints, outputs will be presented by pre-vaccination HAI antibody titer (<1:10 or ≥ 1:10).

## 9. DISPOSITION AND WITHDRAWALS

All subjects who are screened will be accounted for in this study.

Subject disposition, including the number (n) and percentage (%) of subjects in each treatment arm who completed the study and prematurely discontinued study participation (including primary reason for premature study discontinuation), will be tabulated for all subjects.

By-subject data listing of the disposition data i.e., age group, site, treatment, study status, completion/discontinuation date, and reason for discontinuation will be presented.

Frequency and percentage of subjects having critical, major and minor protocol deviations (see [Appendix 1](#)) will be presented by deviation category in vaccine, placebo and overall for all subjects in the FA Population. Subjects having multiple reasons for exclusion will be counted only once per each reason documented.

## 10. DEMOGRAPHIC AND OTHER BASELINE CHARACTERISTICS

Demographic data and other baseline characteristics will be presented both in summaries (by treatment group and overall) for the FA population and in listings for the Enrolled population.

No statistical testing will be performed for demographic or other baseline characteristics.

The following demographic and other baseline characteristics will be reported for this study:

- Age (years)
- Sex
- Ethnicity

### 10.1 DERIVATIONS

For randomized subjects, age is calculated as the number of years from the date of birth to randomization date.

---

Document:	\\EEDC-NAS01A\Biosdata\Path\IVACFLU-S\IYA06804\Biostatistics		
	Documentation\SAP\IVACFLU-S-0203_SAP_Draft v1.0		
Author:	[name]	Version Number:	1.0
		Version Date:	[11AUG2017]
Template No:	CS_TP_BS016 Revision 4	Reference:	CS_WI_BS005
Effective Date:	01Apr2016		

## 11. CURRENT MEDICAL CONDITIONS

Current Medical Condition information will be presented for the FA population for summarising and listing the data. Current Medical Conditions will be coded using MedDRA dictionary version 20.0. The Current Medical Condition categories captured in the eCRF will be presented by system organ class (SOC) and preferred term (PT). The summaries will be presented by primary SOC and PT for vaccine, placebo and overall for all subjects in the FA population. A subject will be counted only once within the SOC and PT if the subject has multiple medical conditions within the same SOC and PT.

A listing of current medical conditions will also be generated.

## 12. MEDICATIONS

Medications will be presented for the FA population and are not coded.

Frequency and percentage of subjects receiving concomitant medications will be summarized by vaccine and placebo for each reported term.

A subject will be counted only once under reported term if the subject receives same concomitant medication multiple times.

By-subject listing of the data will be presented for the FA population.

## 13. STUDY MEDICATION EXPOSURE

The date and time of vaccination and location of vaccination will be presented in the listings.

## 14. STUDY MEDICATION COMPLIANCE

Not applicable for this study.

## 15. EFFICACY OUTCOMES

Not applicable for this study.

---

Document:	\\EEDC-NAS01A\Biosdata\Path\IVACFLU-S\IYA06804\Biostatistics		
	Documentation\SAP\IVACFLU-S-0203_SAP_Draft v1.0		
Author:	[name]	Version Number:	1.0
		Version Date:	[11AUG2017]
Template No:	CS_TP_BS016 Revision 4	Reference:	CS_WI_BS005
Effective Date:	01Apr2016		

## 16. IMMUNOGENICITY ANALYSIS

### 16.1 STATISTICAL CONSIDERATIONS

The Vietnam MOH guidance on serological immune response requirements for influenza vaccine is a modification of the EMEA/CPMP serological criteria for assessing seasonal influenza for licensure. The age-group specific MOH licensure requirements for influenza vaccine in adults are shown in Table 3.

Table 3 Vietnam MOH Criteria for Evaluation of Influenza Vaccine Immune Responses

	Age Group	
	18 – 45	46
Proportion achieving a HAI titer $\geq$ 1:40 (seroprotection)	$\geq$ 70%	$\geq$ 60%
Proportion achieving at least 4 fold rise in HAI titer (seroconversion)	$\geq$ 40%	$\geq$ 30%
GMT rise in HAI titer	$\geq$ 2.5 times	$\geq$ 2.0 times

Null hypothesis ( $H_0$ ):

A single dose of IVACFLU-S seasonal trivalent split, inactivated influenza vaccine will not induce immune responses to each of the three vaccine antigens to meet one or both age group specific Vietnam Ministry of Health licensure requirements i.e., as mentioned in Table 3.

Alternative hypothesis ( $H_1$ ):

A single dose of IVACFLU-S seasonal trivalent split, inactivated influenza vaccine will induce immune responses to each of the three vaccine antigens to meet one or both age group specific Vietnam Ministry of Health licensure requirements i.e., as mentioned in Table 3.

Of the three criteria, seroconversion has been the most frequent criteria not meeting licensure threshold. Though the study assumption is based on Phase 1 immunogenicity data for adults 18-45 years of age, we anticipate the immune response in those 46 - 60 will be comparable since significant decline in antibody response is most associated with those who are  $\geq$ 65 years of age.

Taken together with the immunogenicity results of the IVACFLU-S phase 1 study (refer to [Section 2.1.6](#) in the protocol), the sample size consideration for immunogenicity for the study was based on the precision of the estimate of percent of vaccine recipients with HAI seroconversion and seroprotection responses. With a sample size of 100 evaluable vaccine recipients from each age group, the study provides the precision of immunogenicity response as estimated by width of 95% CI of  $\leq \pm 10.2\%$  around the range of estimated response rate ([Table 4](#))

Document:	\\EEDC-NAS01A\Biosdata\Path\IVACFLU-S\IYA06804\Biostatistics		
	Documentation\SAP\IVACFLU-S-0203_SAP_Draft v1.0		
Author:	[name]	Version Number:	1.0
		Version Date:	[11AUG2017]
Template No:	CS_TP_BS016 Revision 4	Reference:	CS_WI_BS005
Effective Date:	01Apr2016		

Table 4: Observed Response Rate in 100 participants receiving study vaccine and Corresponding 95% CI.

Number of responders (%)	2-sided exact 95% CI
90 (90%)	[82.4%, 95.1%]
80 (80%)	[70.8%, 87.3%]
70 (70%)	[60.0%, 78.8%]
60 (60%)	[49.7%, 69.7%]
50 (50%)	[39.8%, 60.2%]
40 (40%)	[30.3%, 50.3%]
30 (30%)	[21.2%, 39.9%]

An increase in sample size by 50% to 150 provides very limited statistical benefit as it only reduces the maximal width of 95% CI by 1.9% to  $\leq \pm 8.3\%$ . All power calculations were made using 10000 simulations of binomial responses to each strain, based on assumed true response rates and pass/fail criteria. All calculations were made using SAS version 9.3.

